### **10.5. Definition of an Adverse Event**

An AE is any untoward medical occurrence in a clinical investigation subject administered a pharmaceutical product and which is not necessarily required to have a causal relationship with this treatment. An AE can therefore be any unfavorable and unintended sign, symptom, or disease temporally associated with the use of a medicinal product, whether or not considered related to the medicinal product. Examples of AEs include:

- Abnormal test findings.
- Clinically significant symptoms and signs.
- Changes in physical examination findings which are untoward and deemed clinically significant by the investigator.
- Allergy/hypersensitivity.

The criteria for determining whether an abnormal objective test finding may be reported as an AE are as follows:

- Test result is associated with accompanying symptoms,
- Test result requires additional diagnostic testing or medical/surgical intervention,
- Test result leads to a change in study dosing or discontinuation from the study, significant additional concomitant drug treatment or other treatment.

- Test result is considered to be an AE by the investigator or Sponsor.

Repeat of a test based on an abnormal result in the absence of the above conditions does not constitute an AE. Any abnormal test result determined to be an error does not require reporting as an AE.

A treatment-emergent AE (TEAE) is an AE that either commenced following initiation of study treatment or was present prior to study treatment but increased in frequency or severity following initiation of study treatment.

Standard medical terminology should be used in describing AEs. Informal descriptions should be avoided.

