## **10.6. Reporting Adverse Events**

All observed or volunteered AEs regardless of treatment group or suspected causal relationship to the study treatment will be reported with two exceptions. Since it is being experimentally induced in this study, hypoglycemia will not be considered an AE in this study unless the event meets one of the definitions of an SAE (see Section 10.8). Injection site reactions will not be considered an AE unless a skin reaction or pain requires medical intervention.

For all AEs, the investigator must pursue and attempt to obtain information adequate to determine the outcome of the AE and to assess whether it meets the FDA criteria for classification as an SAE, requiring immediate notification to Xeris Pharmaceuticals. For AEs with a causal relationship to the investigational product, follow-up by the investigator is required until the event resolves or stabilizes at a level acceptable to the investigator to consider it closed, and Xeris Pharmaceuticals should concur with that assessment.

As part of ongoing safety reviews conducted by the Sponsor, the Sponsor may escalate any non-serious adverse event that is determined to be serious (according to the FDA definitions of an SAE). To assist in the determination of case seriousness, further information may be requested from the investigator to provide clarity and understanding of the event in the context of the clinical study.

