## **16. PROCEDURES FOR MODIFYING THE PROTOCOL OR TERMINATING THE STUDY**

### **16.1. Protocol Modifications and Deviations**

The principal investigator must sign this protocol and its amendments (if any) before initiating the study at a particular site. The investigator will make all reasonable efforts to comply with the written protocol. Protocol modifications to ongoing studies that affect the safety of subjects or that alter the scope of the investigation, the scientific quality of the study, the experimental design, dosing, study assessments, the number of subjects exposed to test drug, or subject selection criteria must be made only after consultation between Xeris Pharmaceuticals and the investigator. All protocol modifications must be reviewed and approved by the IRB before the revised protocol can be implemented. Emergency revisions that eliminate an apparent hazard to subjects do not require preapproval by the IRB. However, the IRB must be notified in writing as soon as possible after the modification has been made. A copy of this communication must be forwarded to Xeris Pharmaceuticals. All departures from the protocol must be fully documented in the source documents and the CRFs of the subjects involved.

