### **7.2.12 Local Tolerability**

#### **7.2.12.1 Injection Site Discomfort Assessment**

This assessment consists of a

- Visual Analog Scale (VAS) (0-100mm)
- Delivery Site Discomfort Description and Duration questionnaire that consists of the following questions:
  - Discomfort question with the following categories: Pain, Itching, (Tingling, twitching or numbness), Irritation and Other.
  - Question regarding how long after administration did the discomfort start and how long it lasted.

This assessment is administered at visit 3 (Day 1, Baseline) and Visit 4 (Day 7) with the VAS scale being administered at several timepoints and the discomfort questionnaire being administered at 10 mins following delivery of study drug.

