## 7.4 Subject Disposition

Subject disposition will be summarized as follows:

- The number of subjects who were screened, screen failures, randomized and who are in each analysis population will be summarized by treatment group and overall.
- The number of early withdrawals and the reasons for withdrawals will be tabulated by treatment group and overall for ITT population

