#### 7.11.1 Adverse Events

A treatment emergent adverse event (TEAE) is defined as:

- Any AE that has an onset on or after the first dose of study drug or
- Any pre-existing AE that has worsened in severity on or after the first dose of study drug.

A treatment-related AE is defined as an AE as being related to the study drug if response to “Is there a reasonable possibility that the drug caused the event?” is Yes. If an AE has missing relationship it is assumed to be related to the study drug for analysis purposes.

Maximum severity will be assumed for an AE with missing severity.

The following tables will be presented for AEs:

- Overall incidence and the number of AEs, SAEs, TEAEs leading to withdrawal.
- TEAE by system organ class and preferred term, incidence and number of events
- Treatment-related TEAE by system organ class and preferred term, incidence and number of events
- Serious TEAE by system organ class and preferred term, incidence and number of events
- TEAE by system organ class, preferred term and maximum severity, incidence
- Treatment related TEAE by system organ class, preferred term and maximum severity, incidence
- TEAEs leading to early withdrawal by system organ class and preferred term, incidence
- Listing of Serious TEAEs (presented in the Table section of the appendices)
- Listing of Deaths (presented in the Table section of the appendices)

All AEs will be listed.

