14.2.2.7.2.1*	Change from Induction 1 (Baseline visit) in Average Neuroglycopenic Scores (ANS), Average Autonomic Scores (AAS) and Average Total Scores (ATS) with PG <50 mg/dl Intent-to-Treat Population	14.2.2.7.1.1
14.2.2.7.2.2*	Change from Induction 1 (Baseline visit) in Average Neuroglycopenic Scores (ANS), Average Autonomic Scores (AAS) and Average Total Scores (ATS) with PG <50 mg/dl Per Protocol Population	14.2.2.7.1.1
14.2.2.8.1.1	Summary of Overall Assessment of Hypoglycemia with PG <70 mg/dl Intent-to-Treat Population	
14.2.2.8.1.2	Summary of Overall Assessment of Hypoglycemia with PG <70 mg/dl Per Protocol Population	14.2.2.8.1.1
14.2.2.8.2.1	Summary of Overall Assessment of Hypoglycemia with PG <50 mg/dl Intent-to-Treat Population	14.2.2.8.1.1
14.2.2.8.2.2	Summary of Overall Assessment of Hypoglycemia with PG <50 mg/dl Per Protocol Population	14.2.2.8.1.1
14.2.2.9.1.1	Change from Baseline in CGM-Derived Hypoglycemia Parameters by Day - Intent-to-Treat Population	
14.2.2.9.1.2	Change from Baseline in CGM-Derived Hypoglycemia Parameters by Day - Per Protocol Population	14.2.2.9.1.1
14.2.2.9.2.1	Change from Baseline in CGM-Derived Hypoglycemia Parameters by Week - Intent-to-Treat Population	14.2.2.9.1.1
14.2.2.9.2.2	Change from Baseline in CGM-Derived Hypoglycemia Parameters by Week - Per Protocol Population	14.2.2.9.1.1
14.2.2.10.1*	Change from Induction 1 (Baseline visit) in Gold Scale Assessment of Hypoglycemia Unawareness - Intent-to-Treat Population	
14.2.2.10.2*	Change from Induction 1 (Baseline visit) in Gold Scale Assessment of Hypoglycemia Unawareness - Per Protocol Population	14.2.2.10.1
14.3.1.1*	Overview of Adverse Events - Safety Population	
14.3.1.2*	Summary of Treatment-Emergent Adverse Events by System Organ Class, Preferred Term - Safety Population	
14.3.1.3	Summary of Treatment-related Treatment-Emergent Adverse Events by System Organ Class, Preferred Term - Safety Population	14.3.1.2
14.3.1.4*	Summary of Serious Treatment-Emergent Adverse Events by System Organ Class, Preferred Term - Safety Population	14.3.1.2
14.3.1.5	Summary of Treatment-Emergent Adverse Events Leading to Study Discontinuation by System Organ Class, Preferred Term - Safety Population	14.3.1.2

Table Number	Table Title	Shell Number (if repeat)
14.3.1.6	Summary of Serious Adverse Events Leading to Death by System Organ Class, Preferred Term - Safety Population	14.3.1.2

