16.2.5.1	Study Drug Administration Intent-to-Treat Population	
16.2.5.2	Euglycemic Baseline and Hypoglycemia Induction Intent-to-Treat Population	
16.2.5.3*	Plasma Blood Glucose during Euglycemic Maintenance, Hypoglycemia Induction and Stabilization, and Normalization to Euglycemia All Subjects	
16.2.5.4	Plasma Blood Glucose Levels from Plasma Glucose Screener Intent-to-Treat Population	
16.2.6.1	Subject Insulin Diary Safety Population	
16.2.6.2.1	Interstitial Glucose Parameters During CGM Monitoring All Subjects	
16.2.6.3.1	Average Glucose Infusion Rate to Maintain Glucose at 50 mg/dL for the first 30 minutes after 50 mg/dL Achieved during Hypoglycemia Stabilization All Subjects	
16.2.6.3.2	Cumulative Glucose Infusion to Maintain Glucose at 50 mg/dL for the first 30 minutes after 50 mg/dL Achieved during Hypoglycemia Stabilization All Subjects	
16.2.6.4.1.1	Hypoglycemia Symptom Questionnaire Responses After Achieving Plasma Glucose of < 70 mg/dL All Subjects	
16.2.6.4.1.2*	Hypoglycemia Symptom Questionnaire Responses After Achieving Plasma Glucose of < 50 mg/dL All Subjects	

Listing Number	Listing Title	Shell Number (if repeat)
16.2.6.4.2.1	Average Neuroglycopenic, Autonomic and Total Symptom Scores After Achieving Plasma Glucose of < 70 mg/dL All Subjects	
16.2.6.4.2.2*	Average Neuroglycopenic, Autonomic and Total Symptom Scores After Achieving Plasma Glucose of < 50 mg/dL All Subjects	
16.2.6.4.3.1	Overall Assessment of Hypoglycemia After Achieving Plasma Glucose of < 70 mg/dL All Subjects	
16.2.6.4.3.2	Overall Assessment of Hypoglycemia After Achieving Plasma Glucose of < 50 mg/dL All Subjects	
16.2.6.4.4	Gold Scale of Hypoglycemia Unawareness All Subjects	
16.2.7*	Adverse Events All Patients	
16.2.8.1*	Hormones and Counter Regulatory Hormone Response All Patients	
16.2.8.2	Serum Concentration of Glucagon during CSGI Treatment All Patients	
16.2.8.3	Serum and Plasma Concentration of Glucagon Antibodies All Patients	
16.2.8.4	Clinical Laboratory Results: Hematology All Patients	
16.2.8.5	Laboratory Results: Chemistry, Complete Metabolic Panel Safety Population	
16.2.8.6	Laboratory Results: Drug Screen All Patients	
16.2.8.7	Listing of Laboratory Results: Serology Intent-to-Treat Population	
16.2.8.8	Urine Pregnancy Test Results All Patients	
16.2.9.1	Injection Site Discomfort - Visual Analog Scale (VAS) Safety Population	

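### Protocol 10.6 does not require an AE record for an untreated injection-site reaction that stops study drug or ends participation, so it may be missing from the TEAE tables

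*Protocol*

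**What the plan says.** Protocol 10.6 reports all AEs with two exceptions. Hypoglycemia is left out unless it meets an SAE definition. The other exception reads: "Injection site reactions will not be considered an AE unless a skin reaction or pain requires medical intervention". The term for intervention is not defined, and stopping drug or leaving the study is not mentioned.

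Protocol 10.5 sets a different rule for abnormal test findings. A need for further testing or intervention is one trigger for an AE, and a separate trigger reads: "Test result leads to a change in study dosing or discontinuation from the study".

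SAP 7.11.1 defines a TEAE as an AE that starts or worsens on or after first dose, and builds its tables from those records. They include "TEAEs leading to early withdrawal by system organ class and preferred term, incidence", which appears in the SAP's table list as Table 14.3.1.5: "Summary of Treatment-Emergent Adverse Events Leading to Study Discontinuation by System Organ Class, Preferred Term".

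Outside the AE system, SAP 7.4 provides: "The number of early withdrawals and the reasons for withdrawals will be tabulated by treatment group and overall for ITT population". Local tolerability is a named safety endpoint (Protocol 5.3.2, SAP 4.2.2), with visual analog scale (VAS), discomfort questionnaire and Draize summaries of its own (SAP 7.11.6).

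**The concern.** This is a four-week continuous subcutaneous infusion. Whether the infusion site becomes bad enough to end treatment is one of the main tolerability questions. A reader will look for the answer in the AE tables, with severity and relatedness attached.

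Under 10.6 a subject could stop the infusion because of site pain, receive no treatment for it, and have no AE form. The withdrawal table could then show no site reactions when there were some. The reader would have to piece the event together from a disposition reason, a listing or a deviation, none of which is planned to carry a causality assessment.

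**Working it through.** No formula applies. The check follows one case through the documents: a non-serious site reaction, given no treatment, that makes the subject stop study drug or leave the study.

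**Step 1. Must it be an AE?** Under Protocol 10.6, no, because the only stated trigger is a need for medical intervention. The trigger for a dosing change or discontinuation in 10.5 applies to test findings and is not repeated for site reactions. The hypoglycemia exception brings serious events back into AE reporting; the site-reaction exception contains no such clause. The list of changes in SAP section 10 does not touch the rule.

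**Step 2. What depends on AE status?**
- The severity grade (Protocol 10.9).
- The causality assessment, which is mandatory for AEs (10.10).
- Follow-up of drug-related events until they resolve or stabilize (10.6), and of AEs unresolved at withdrawal (9.6).
- Classification as a withdrawal due to an AE (10.11).
- Entry into every TEAE table (SAP 7.11.1).

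**Step 3. By what routes could it still become an AE?**
- The investigator may count removing the pod or stopping drug as medical intervention, since the term is undefined.
- Protocol 11.3.3 makes an examination change an AE if the investigator judges it clinically significant, and 10.5 gives the same kind of change as an example. A visible skin reaction could qualify; pain without signs would not. The documents do not say whether 10.6 overrides this.
- Allergy or hypersensitivity is an AE under 10.5.

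Each route depends on the investigator's judgment, so like cases could be recorded differently at different sites.

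**Step 4. Where else would it appear?**
- *Disposition.* The CRF records why a subject did not complete the study (Protocol 9.6), and SAP 7.4 tabulates the reasons by arm. This covers study withdrawal, but not a drug stop in a subject who stays in the study.
- *Exposure.* SAP 7.2.6 ignores breaks in therapy, and SAP section 10 states that treatment compliance data were not captured.
- *Listings and accountability.* Listing 16.2.5.1, "Study Drug Administration Intent-to-Treat Population", or the weekly vial and pod accountability may show a stop.
- *Deviations.* Protocol 16.1 says: "All departures from the protocol must be fully documented in the source documents and the CRFs of the subjects involved". A stop recorded as a deviation would be listed.
- *Local scores.* VAS, discomfort and Draize results grade local severity. No planned output links a score to the decision to stop, and SAP 7.2.8 tabulates only scheduled post-baseline tolerability values.

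None of these routes calls for a causality assessment tied to the stop.

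**Step 5. Scale.** The documents give no expected rate. With the planned 16 subjects per arm (Protocol 8.4), one such withdrawal is 1/16 = 6.25% of an arm, or 1/32 = 3.1% of the combined CSGI group. These figures show what one subject weighs; they do not estimate frequency.

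**The case against.** The strongest reply is that the plan handles site reactions by a deliberate separate route. They have their own instruments, tables and listings, and study withdrawals are tabulated by reason and arm. Routine mild reactions can reasonably stay outside AE reporting. The case at issue is also narrow: the reaction must end or interrupt treatment, go untreated, be non-serious, and not be reported as hypersensitivity or as an examination change. Pods are replaced every two to three days, so a reaction at one site is not in itself a reason to stop drug.

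Most of this stands, and it rules out three stronger readings that a reader might infer.

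- *Such a reaction can never have an AE record.* The documents do not support this. The undefined term in 10.6, the examination rule in 11.3.3 and the hypersensitivity example in 10.5 each leave a way in. The defect is that the record is not required.
- *The event disappears from the report.* A study withdrawal would still appear in the disposition table, and a drug stop may appear in a listing, in accountability records or as a deviation.
- *The visits named in SAP 7.2.12 measure the size of the gap.* They do not. The protocol's visit text asks for VAS and discomfort scoring at each pod start and makes Visits 5 and 6 identical to Visit 4, so further scores may exist. Any mismatch between the SAP and the protocol on visit coverage is a separate matter.

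The separate route still does not supply a severity grade and causality assessment tied to the decision to stop. The ways into AE status also make recording depend on the site, which is itself a reason to settle the rule.

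**Conclusion.** The point holds as a gap in what must be reported. An untreated, non-serious injection-site reaction that interrupts or ends study drug, or leads to withdrawal, may have no AE record, and may then be missing from the TEAE tables and from the table of TEAEs leading to withdrawal. Whether it is recorded depends on how each investigator reads 10.6 and 11.3.3.

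The size is unknown because the documents give no event rate. A reader might infer that the rule flatters the active arms. The documents do not show this: the exception applies to every arm, and placebo is the vehicle delivered at matched rates (Protocol 8.4, 8.6.1.2). No effect on the primary epinephrine analysis is shown. The conclusion rests on the text of 10.6 and on SAP 7.11.1 building its tables from AE records. The change is a cheap improvement to the safety reporting.

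**What to change.** Amend Protocol 10.6 so that an injection-site reaction is an AE if any of the following applies:
- it requires medical intervention;
- it leads to interruption or discontinuation of study drug, other than merely re-siting or replacing a pod while infusion continues;
- it leads to withdrawal from the study;
- it meets an SAE criterion.

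State that this rule governs over 11.3.3 for findings at the infusion site. Study withdrawals then enter the existing withdrawal table. That table covers study discontinuation only, so add a flag for action taken with study drug to the AE listing (16.2.7) to show drug-only stops.

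The cost is a short protocol amendment with IRB approval, a few more AE forms and a slightly less favorable AE count. The AE form is not in the documents; if it does not already collect action taken with study drug, it needs one field. If subjects are already enrolled, apply the rule to all of them by reviewing recorded withdrawals and drug stops, so that two AE definitions are not mixed in one table.

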## **10.7. Reporting Period**

For all AEs, the reporting period to Xeris Pharmaceuticals begins from the subject providing informed consent, through the last subject Visit. All adverse events will be followed until resolution or the subject is medically stable.

## **10.8. Serious Adverse Events**

An SAE is any untoward medical occurrence which:

- Results in death.
- Is life-threatening.
- Requires inpatient hospitalization or extends hospitalization.
- Results in persistent or significant disability.
- Is another important medical event.

Medical and scientific judgment is exercised in determining whether an event is an important medical event. An important medical event may not be immediately life-threatening and/or result in hospitalization or death. However, if it is determined that the event may jeopardize the subject or may require intervention to prevent a SAE outcome, the important medical event should be reported as serious. Examples of such events are intensive treatment in an emergency room or at home for allergic bronchospasm or blood dyscrasias or convulsions which do not result in hospitalization.

### 10.9. Severity Assessment

On the AE case report forms (CRF), the investigator will use the adjectives “mild,” “moderate,” or “severe” to describe the maximum intensity of the AE. These intensity grades are defined as follows in [Table 9](#) below.

**Table 9: AE Severity Assessment**

Mild	Does not interfere with subject’s usual function
Moderate	Interferes to some extent (<50%) with subject’s usual function
Severe	Interferes significantly (≥50%) with subject’s usual function

The terms “serious” and “severe” are not synonymous. The term “severe” is often used to describe the intensity (severity) of a specific event. The event itself, however, may be of relatively minor medical significance. This is not the same as “serious,” which is based on subject/event outcome or action criteria. Accordingly, a severe event is not necessarily a serious event.

### 10.10. Causality Assessment

The investigator will use the following question when assessing causality of an adverse event to study drug, where an affirmative answer designates the event as a suspected adverse reaction: “Is there a reasonable possibility that the drug caused the event?” A “reasonable possibility” means that there is evidence to suggest a causal relationship between the drug and the adverse event. The investigator’s assessment of causality must be provided for all AEs. The investigator must record the causal relationship in the CRF, as appropriate, and report such an assessment in accordance with the serious adverse event reporting requirements, if applicable.

### 10.11. Withdrawal Due to Adverse Events

Withdrawal due to AE should be distinguished from withdrawal due to insufficient response, and recorded on the appropriate CRF. When a subject withdraws due to an SAE, the SAE must be reported in accordance with the reporting requirements (see [Section 10.13](#)).

### 10.12. Eliciting Adverse Event Information and Reporting

The investigator is to report all directly observed AEs and all AEs spontaneously reported by the study subject. Each study subject will be questioned about AEs. Each AE is to be assessed to

determine if it meets the criteria for SAEs. If an SAE occurs, expedited reporting will follow the provisions of Section 10.13.

